6.2 Evaluation of pharmacokinetics

The analysis and reporting of PK data and parameters are beyond the scope of this SAP. A separate analysis plan is planned to be developed for this analysis and a final report will be provided under separate cover.

6.3 Evaluation of immunogenicity

The analysis and report of Anti-drug antibody will be provided under separate cover as well as PK.

7. Evaluation of Efficacy

	Forms			
	Title	Statistical Analysis Plan Template		
	Code	Version	Effective Date	Page
	FRM_ST03_032	01	23 Apr 2015	28 of 53

The efficacy endpoints will be evaluated in FAS population and results will be presented in listings and tables. Continuous variables will be tabulated with descriptive statistics. Categorical measures will be summarized as number and percentage of subjects.

7.1 Analysis of primary endpoint

The primary efficacy endpoint is the mean change in mucosal score presented by mMES (subscores from 0 to 3 with modified endoscopy finding scoring, i.e., excluding mild friability from a subscore of 1) from Baseline (Week 0) to Week 12 for all subjects who received the recommended dose during Induction Therapy. This includes Part A subjects who received the recommended dose identified for Part B as well as the subjects who received the recommended dose during Part B of Induction Therapy. Change from Baseline in mMES as well as Baseline and Week 12 will be summarized by treatments (each KHK4083 dose level and placebo) by means of descriptive statistics (number of subject n, mean, standard deviation, median, min and max); the 95% confidence Interval (CI) for the change from baseline will be derived as follow:

$$\text{Upper 95\%CI} = \mu_x + t(\alpha, df)SE(\mu_x)$$

$$\text{Lower 95\%CI} = \mu_x - t(\alpha, df)SE(\mu_x)$$

where:

- μ_x is the arithmetic mean estimate of the change from baseline
- t is the value from a t table distribution with $\alpha = 0.05$ and df degree of freedom

SE is the Standard error of the mean estimate.

A comparison between treatments (each KHK4083 dose level versus placebo) will be performed using an ANCOVA model with change from Baseline in mMES as dependent variable and treatment as fixed effect and baseline value as covariate. The number of subjects and the number of subjects considered in the model will be provided by treatment. The adjusted means for treatments (least squares means) and the relative 95% CIs will be presented. The difference between the adjusted means for each treatment groups from placebo (Difference in Least Squares Mean from Placebo) will be calculated with the relative 95% CI and p-value. Least squares means with 95% CIs and differences in least squares mean from placebo with 95% CIs will be graphically presented.

In order to test for optimal dose levels within this fitted linear model, three types of contrasts will be defined to demonstrate which KHK4083 dose level is deemed closest to optimal. The first contrast is for the scenario of “10 mg/kg is closest to optimal” and its vector, (P L M H), is (-1 -1 -1 3), where P: Placebo; L: 1.0 mg/kg; M: 3.0 mg/kg; and H: 10 kg/mg. The second contrast is for the scenario of “3.0 mg/kg is closest to optimal” and its vector is (-1 -1 1 1). The third contrast is for the scenario of “1.0 mg/kg is closest to optimal” and its vector is (-3 1 1 1). Each contrast will be tested within the fitted model to determine the dose level providing optimum benefit over placebo.

SAS® code

```
Proc GLM data=dataset;
Class tmt;
Model change=tmt baseline / solution clparm;
```

	Forms			
	Title	Statistical Analysis Plan Template		
	Code	Version	Effective Date	Page
	FRM_ST03_032	01	23 Apr 2015	29 of 53

```

Lsmeans tmt/cl stderr;
Estimate "1.0 mg Vs Placebo" tmt -1 1 0 0;
Estimate "3.0 mg Vs Placebo" tmt -1 0 1 0;
Estimate "10 mg Vs Placebo" tmt -1 0 0 1;
Contrast "1.0 mg is closest to optimal" tmt -3 1 1 1;
Contrast "3.0 mg is closest to optimal" tmt -1 -1 1 1;
Contrast "10 mg is closest to optimal" tmt -1 -1 -1 3;
Run;

```

	Forms			
	Title	Statistical Analysis Plan Template		
	Code	Version	Effective Date	Page
	FRM_ST03_032	01	23 Apr 2015	30 of 53

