12.3.5 Significance Level

All statistical analyses in this Phase 2 study will be descriptive or exploratory, and no adjustment to control Type I error will be performed.

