Statistical hypothetical testing will not be carried in this study. However, in the case that p-value is derived, it will be rounded to three decimal places.

All statistical analyses will be performed using Statistical Analysis System (SAS) statistical software (Version 9.2 or higher). AEs will be coded for summarization using Medical Dictionary for Regulatory Activities (MedDRA® Version 18.1). Concomitant medications will be coded using WHO Drug Dictionary (enhanced) 1st Q2015 B-format.

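### The three dose contrasts for Week 12 mMES cannot identify the dose with optimum benefit over placebo, which is the purpose the plan gives them

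*SAP*

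**What the plan says.** The primary comparison is made "using an ANCOVA model with change from Baseline in mMES as dependent variable and treatment as fixed effect and baseline value as covariate" (SAP 7.1). Three contrasts over placebo, 1.0, 3.0 and 10 mg/kg are then defined in that model:

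- (-1 -1 -1 3), for the scenario that 10 mg/kg is closest to optimal;
- (-1 -1 1 1), for 3.0 mg/kg;
- (-3 1 1 1), for 1.0 mg/kg.

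The section concludes: "Each contrast will be tested within the fitted model to determine the dose level providing optimum benefit over placebo". Protocol 12.3.1 has the same contrasts and the same closing sentence. The SAS code in SAP 7.1 runs them as CONTRAST statements. In the same block, three ESTIMATE statements compare each dose with placebo.

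Neither document gives an alpha, a direction, an order of testing, or a rule for several significant contrasts or none. Protocol 12.3.5 says "no adjustment to control Type I error will be performed". SAP 4.1 says "Statistical hypothetical testing will not be carried in this study", which leaves the status of these tests unclear.

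**The concern.** The plan ties a specific conclusion, the dose with optimum benefit over placebo, to three separate tests. For that to work, each test would have to measure benefit over placebo, and the tests would have to separate the doses. Neither holds. Two of the contrasts can be non-zero when the named dose is no better than placebo, and a single true dose-response shape moves all three at once. An F test also does not distinguish improvement (a negative change in mMES) from worsening.

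At stake is how the primary-endpoint output is worded. A row labelled with a dose as closest to optimal and carrying a small p-value invites a claim that the test does not support. If several rows are significant, the choice among them would be made after unblinding.

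**Working it through.** **The plan's own figure.** The documents state no operating characteristic for the contrasts. The only figure to reproduce is the sample size: 60 × 0.85 = 51 evaluable, with 9 + 18 = 27 on the recommended dose and 9 + 6 = 15 on placebo (SAP 3.2).

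**Inputs.** Contrast vectors and model come from SAP 7.1. Applying 85% to 15/9/9/27 gives 12.75/7.65/7.65/22.95, taken as 13/8/8/22 so that the total is 51. *Assumptions, not in the documents:* 10 mg/kg is the recommended dose; two-sided 5% per contrast; normal errors; full effects of 0.5 to 1.0 SD. Residual df = 51 − 5 = 46.

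**Step 1: comparators.** Divided by 3, (-1 -1 -1 3) is 10 mg/kg minus the average of placebo, 1.0 and 3.0 mg/kg. Divided by 2, (-1 -1 1 1) is the average of 3.0 and 10 mg/kg minus the average of placebo and 1.0 mg/kg. Only (-3 1 1 1) has placebo as sole comparator, and it pools all three doses on the active side. This is algebra and needs no effect size.

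**Step 2: overlap.** SE of a contrast in SD units = √Σ(c²/n):

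- 10 mg/kg contrast: √(1/13 + 1/8 + 1/8 + 9/22) = 0.858
- 3.0 mg/kg contrast: √(1/13 + 1/8 + 1/8 + 1/22) = 0.610
- 1.0 mg/kg contrast: √(9/13 + 1/8 + 1/8 + 1/22) = 0.994

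Contrast values for a full effect of −1 SD, with |value|/SE in brackets:

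| True shape (P, L, M, H) | 10 mg/kg contrast | 3.0 mg/kg contrast | 1.0 mg/kg contrast |
|---|---|---|---|
| Step at 10: (0, 0, 0, −1) | −3 (3.50) | −1 (1.64) | −1 (1.01) |
| Step at 3.0: (0, 0, −1, −1) | −2 (2.33) | −2 (3.28) | −2 (2.01) |
| Step at 1.0: (0, −1, −1, −1) | −1 (1.17) | −1 (1.64) | −3 (3.02) |
| Linear in rank | −2 (2.33) | −1.33 (2.19) | −2 (2.01) |
| Peak at 3.0: (0, −0.5, −1, −0.5) | 0 (0) | −1 (1.64) | −2 (2.01) |

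No step shape leaves any contrast at zero, so significance cannot single out one dose.

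**Step 3: how often two or more are significant together** (simulation, counted in the direction of improvement):

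| Full effect | Step at 10 | Step at 3.0 | Step at 1.0 |
|---|---|---|---|
| 0.5 SD | 11% | 20% | 11% |
| 0.75 SD | 25% | 47% | 24% |
| 1.0 SD | 41% | 75% | 42% |

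For a linear response reaching 1.0 SD the figure is 58%; with no effect it is about 1%. If the larger group sits at 3.0 or 1.0 mg/kg instead, the 1.0 SD row becomes 35–39%, 61–62% and 36–39%. With all 60 randomized subjects (15/9/9/27), the 0.75 SD row is about 28/54/28%.

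**Step 4: a significant contrast without benefit over placebo (stress case).** Let 10 mg/kg equal placebo and both lower doses be worse by e. The 10 mg/kg contrast is then −2e. At e = 0.5 SD the noncentrality is 1.0/0.858 = 1.17, and the contrast is significant in about 21% of trials. At e = 0.75 SD it is 1.5/0.858 = 1.75, giving about 40%.

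**Step 5: would the largest statistic rescue it?** For step shapes, taking the largest standardised statistic picks the intended contrast in about 74–95% of significant runs at 1.0 SD. For the peak at 3.0 mg/kg, the 1.0 mg/kg contrast has the larger expected statistic (2.01 against 1.64) and is picked in about 60–65% of significant runs at 0.75–1.0 SD. For a linear response the three expected statistics are nearly equal, so the pick is close to arbitrary.

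**The case against.** These are recognisable step-shape contrasts, and pooling lower doses with placebo is how a step is coded. As shape checks they are legitimate. The analysis is labelled exploratory, without Type I error control.

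The information the contrasts lack is already planned. SAP 7.1 requires each dose's LS-mean difference from placebo with a 95% CI and p-value, from the same model, and plots it. In the stress case, that CI favours 10 mg/kg over placebo in only about 2.5% of runs. All of this stands, and it limits the consequence. It does not rescue the sentence, because both documents attach the optimum-benefit conclusion to the contrasts and not to those estimates.

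Three stronger readings are tempting but unsupported:

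- *The contrasts choose the dose carried forward.* The Part B dose is selected on Part A safety data (Protocol 8.1.4.1).
- *They drive the proof-of-concept decision.* SAP 4.5 bases that decision on the Week 12 results. The mMES model is among them (SAP 9.4.1), but nothing links the decision to the contrasts.
- *A harmful dose would pass as optimal.* The F test carries no sign, but the LS means and dose-versus-placebo differences from the same model would show the direction.

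**Conclusion.** The concern holds as a mismatch between stated purpose and procedure. That only one contrast has placebo as sole comparator, and that all three are non-zero under every step shape, follows from the vectors alone. How often contrasts are significant together depends on an effect size the documents do not give: from 11–20% at 0.5 SD to 41–75% at 1.0 SD for step shapes, on the assumptions listed. A reader might infer that multiple significance is the usual outcome; that is so only for some shapes at the upper end of this range. The 21–40% in the stress case requires both lower doses to be worse than placebo, which nothing in the documents suggests.

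The effect is on the wording and interpretation of an exploratory primary-endpoint analysis. It does not affect dose selection for Part B or the dose-versus-placebo estimates. A correction is worth making because the text promises a conclusion the tests cannot give and states no selection rule.

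**What to change.** In SAP 7.1 and Protocol 12.3.1:

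1. Relabel the three contrasts as dose-response shape checks.
2. Report each with an ESTIMATE statement, giving sign and 95% CI. The MODEL statement already has CLPARM; divisors of 3, 2 and 3 would put the results on the mMES scale.
3. Base any statement of benefit over placebo on each dose's already planned LS-mean difference and CI.
4. Delete the clause claiming to determine the dose with optimum benefit over placebo.
5. If a best-fitting shape is to be named, state in advance that it is the one with the largest standardised statistic in the direction of improvement, as description only, with a note that this is unreliable for linear or peaked responses.

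The cost is three lines of code and a few sentences, with no new data. If the protocol is not amended, the change can be reported as a deviation under Protocol 12.8. The downside is a weaker dose claim.

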7.2 Analysis of secondary efficacy endpoints

The secondary efficacy variables for all subjects (i.e., recommended dose or any other dose level in Parts A and B of Induction Therapy) are listed in the following table.

Efficacy Variables	Definition
Improvement in the Mucosa (Measured by modified Mayo endoscopy subscore [mMES]) (Week 12)	Percentage of subjects with at least a 1-point improvement in their mMES (0 to 3) from Baseline (Week 0) to Week 12.
Improvement in the Mucosa (Measured by modified Baron scoring system) (Week 12)	Percentage of subjects with at least a 1-point improvement in their modified Baron endoscopic score (5-point scale) from Baseline (Week 0) to Week 12.
Improvement in the Mucosa (Measured by Ulcerative Colitis Endoscopic Index of Severity [UCEIS]) (Week 12)	A mean change in the UCEIS (scores from 0 to 8, based on findings of vascular pattern, bleeding, and erosions/ulcers) from Baseline (Week 0) to Week 12.
Mucosal Healing (Week 12)	The percentage of subjects with mMES of 0 or 1 at Week 12.
Clinical Improvement (Week 12)	Mean change from Baseline (Week 0) at Week 12, in the total Mayo Clinic score (0 to 12).
Clinical Improvement (Weeks 2, 4, 6, 8, 10, and 12)	Mean changes from Baseline (Week 0) in the partial (excludes endoscopy subscores) Mayo Clinic score (0 to 10).
Clinical Response (Week 12)	A reduction in the total Mayo Clinic score of at least 3 points and a decrease of at least 30% from Baseline (Week 0) to Week 12, and a reduction in the rectal bleeding subscale of at least 1 point from Baseline (Week 0) to Week 12 or an absolute rectal bleeding score of 0 or 1 at Week 12.
Clinical Remission (Week 12)	A total Mayo Clinic score of ≤ 2 and no subscores > 1 .

All secondary efficacy variables will be summarized by treatments (each KHK4083 dose level and placebo). Change from Baseline in UCEIS, total Mayo Clinic score as well as Baseline and Week 12 will be summarized by treatments. Partial Mayo Clinic scores and changes from Baseline will be summarized from Baseline to Week 12 by treatments. Summaries statistics and 95% CI will be presented and estimated as described in section 7.1 of this SAP.

A comparison between treatments (each KHK4083 dose level versus placebo) will be performed using an ANCOVA model with changes from Baseline in UCEIS, total Mayo Clinic score and partial Mayo Clinic score at Week 12 as dependent variables, treatment as fixed effect and baseline value as covariate. The number of subjects and the number of subjects considered in the model will be provided by treatment. The adjusted means for treatments (least squares means) and the relative 95% CIs will be presented. The difference between the adjusted means for each treatment groups from placebo (Difference in Least Squares Mean from Placebo) will be calculated with the relative 95% CI and p-value. Least squares means with 95% CIs and differences in least squares mean from placebo with 95% CIs will be graphically presented.

	Forms			
	Title	Statistical Analysis Plan Template		
	Code	Version	Effective Date	Page
	FRM_ST03_032	01	23 Apr 2015	31 of 53

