2.2 Secondary objectives

- To determine if KHK4083 at dose levels different than the recommended dose improve the mucosa based on the mMES;
- To determine if any dose level of KHK4083 administered as Induction Therapy will meet the following objectives at Week 12:
 - Improve the mucosa based on the modified Baron endoscopic score;
 - Improve the mucosa based on the Ulcerative Colitis Endoscopic Index of Severity (UCEIS);
 - Induce mucosal healing based on the mMES;
 - Improve clinical signs and symptoms based on total Mayo Clinic score;
 - Improve clinical signs and symptoms based on partial Mayo Clinic scores (Week 2 through Week 12, excludes endoscopy subscores);
 - Induce a clinical response based on a reduction in the total Mayo Clinic score (i.e., reduction of at least 3 points and a decrease of at least 30% from Baseline [Week 0] to Week 12) and rectal bleeding subscale (i.e., reduction of at least 1 point from Baseline [Week 0] to Week 12) (or a defined absolute rectal bleeding score of 0 or 1 at Week 12);
 - Induce clinical remission based on a total Mayo Clinic score (i.e., score of ≤ 2) and subscores (i.e., no subscores > 1).
- To characterize the PK of KHK4083 in subjects with moderately active UC following multiple dose administration;
- To evaluate the development of antibodies against KHK4083 (immunogenicity).

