3.2 Sample size justification

Assuming a 15% dropout rate, it is anticipated that approximately 60 subjects will be required to be randomized in order to achieve 51 evaluable subjects in the full analysis set (FAS). In Part A (Cohorts 1 - 3), the sample size is based on the feasibility of the safety and tolerability assessment to recommend starting the treatment of the next cohort of 12 subjects/cohort (9 subjects to receive KHK4083 and 3 subjects to receive placebo). In Part B (Cohort 4) for the treatment of 24 subjects (18 subjects to receive KHK4083 at the recommended dose based on the safety and tolerability in Part A and 6 subjects to receive placebo), the sample size is based on the feasibility of exploratory assessments in efficacy and safety at the recommended dose level. Based on the UCEIS and Mayo Clinic scores and from combining Part A and Part B, it is planned to have approximately a total of 27 randomized subjects receive the recommended dose of KHK4083 and 15 subjects receive placebo.

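### Five of the eight Week 12 secondary variables are percentages, and the plan gives them neither a difference from placebo nor an interval suited to a proportion

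*SAP*

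**What the plan says.** The secondary objectives in SAP 2.2 open with "To determine if any dose level of KHK4083 administered as Induction Therapy will meet the following objectives at Week 12". The list that follows includes inducing mucosal healing, clinical response and clinical remission, and improving the mucosa on the Baron score.

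SAP 7.2 tabulates eight variables and begins its analysis text with "All secondary efficacy variables will be summarized by treatments (each KHK4083 dose level and placebo". It then describes summaries of the UCEIS, total Mayo and partial Mayo scores and ends the paragraph with "Summaries statistics and 95% CI will be presented and estimated as described in section 7.1 of this SAP". The section referred to, SAP 7.1, introduces one interval: "the 95% confidence Interval (CI) for the change from baseline will be derived as follow", followed by the arithmetic mean plus or minus t times its standard error. The opening of SAP section 7 says that categorical measures are reported as counts and percentages, with no interval mentioned.

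The comparison with placebo in SAP 7.2 is an ANCOVA with "changes from Baseline in UCEIS, total Mayo Clinic score and partial Mayo Clinic score at Week 12 as dependent variables". Protocol 12.3.2 also restricts treatment comparisons to continuous variables.

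Protocol 12.3.5 calls all analyses descriptive or exploratory, and SAP 4.1 says hypothesis testing is not planned. SAP 4.5 says the unblinded Week 12 results will be used to judge proof of concept of efficacy.

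**The concern.** Whether a dose induces healing, response or remission cannot be judged from the percentage in that dose group alone, because some placebo subjects will also meet the criterion. The quantity of interest is the difference from placebo and its uncertainty. The plan supplies this for the continuous scores, with a 95% CI and a p-value, but not for the percentages, which are the more directly clinical outcomes.

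In groups of 9 to 27 subjects a bare percentage is also easy to over-read. Without a pre-specified interval and difference, whoever makes the proof-of-concept judgement must compare percentages by eye or choose a method after unblinding. If a programmer follows the cross-reference to 7.1 literally, the tables could show negative lower limits or zero-width intervals.

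**Working it through.** **1. Count the variables in SAP 7.2.**

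| Variable | Type | Comparison with placebo planned |
|---|---|---|
| mMES improvement by at least 1 point | percentage | none |
| Baron improvement by at least 1 point | percentage | none |
| Mucosal healing | percentage | none |
| Clinical response | percentage | none |
| Clinical remission | percentage | none |
| UCEIS change | mean | ANCOVA |
| Total Mayo change | mean | ANCOVA |
| Partial Mayo change | mean | ANCOVA |

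Five of eight are percentages. The unblinded Week 12 table list (SAP 9.4.1) has the same pattern: the three scores each have an analysis table, while the five percentages share Table 14.2.2.4. Neither document names a difference in proportions, an exact method, a stratified test or a logistic model for them.

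**2. Group sizes.** SAP 3.2 states: "Assuming a 15% dropout rate, it is anticipated that approximately 60 subjects will be required to be randomized in order to achieve 51 evaluable subjects". Check: 51/(1 − 0.15) = 60. It plans "27 randomized subjects receive the recommended dose of KHK4083 and 15 subjects receive placebo", and for each Part A cohort "9 subjects to receive KHK4083 and 3 subjects to receive placebo". Check: 9 + 18 = 27; 3 × 3 + 6 = 15; 27 + 9 + 9 + 15 = 60. The planned figures reproduce. The groups are therefore 27 (recommended dose), 9 (each other dose) and 15 (pooled placebo), or about 23, 8 and 13 after 15% dropout.

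**3. The 7.1 formula, if applied to 0/1 data.** With x responders in n and p = x/n, the standard error is √[p(1 − p)/(n − 1)] and the limits are p ± t(0.975, n − 1) × SE.

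Worked case, 1/9: p = 0.1111; SE = √(0.09877/8) = 0.1111; t = 2.306; half-width 0.2562; limits −14.5% to 36.7%.

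The documents give no response rates, so all counts below are assumed.

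| Count | 7.1 formula (%) | Exact (%) | Wilson (%) |
|---|---|---|---|
| 0/9 | 0.0 to 0.0 | 0.0 to 33.6 | 0.0 to 29.9 |
| 1/9 | −14.5 to 36.7 | 0.3 to 48.2 | 2.0 to 43.5 |
| 3/9 | −5.1 to 71.8 | 7.5 to 70.1 | 12.1 to 64.6 |
| 4/9 | 3.9 to 85.0 | 13.7 to 78.8 | 18.9 to 73.3 |
| 2/15 | −6.2 to 32.8 | 1.7 to 40.5 | 3.7 to 37.9 |
| 4/15 | 1.3 to 52.0 | 7.8 to 55.1 | 10.9 to 52.0 |
| 3/27 | −1.6 to 23.8 | 2.4 to 29.2 | 3.9 to 28.1 |
| 4/27 | 0.5 to 29.1 | 4.2 to 33.7 | 5.9 to 32.5 |

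At all three sizes, limits leave 0–100% at 1 to 3 responders or 1 to 3 non-responders, and the width is zero at 0 or n responders. Other counts stay inside.

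**4. How often this would happen**, by exact binomial sums at assumed true rates.

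| True rate | Result | n = 9 | n = 15 | n = 27 |
|---|---|---|---|---|
| 10% | limit outside 0–100% | 60% | 74% | 66% |
| 10% | zero width | 39% | 21% | 6% |
| 10% | coverage, 7.1 formula | 61% | 79% | 94% |
| 10% | coverage, Wilson | 95% | 94% | 95% |
| 30% | limit outside 0–100% | 72% | 29% | 2% |

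**5. What a planned difference would show.** Assume 11/27 versus 3/15. The difference is 40.7% − 20.0% = 20.7 points. The Newcombe limits, built from the two Wilson intervals, are −9.2 to 43.4 points.

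**The case against.** The strongest reply is that the t interval was never meant for the percentages. The sentence pointing to 7.1 follows text about continuous scores. The 7.1 formula is defined for a mean change from baseline, which healing and remission are not. The opening of section 7 gives categorical measures only a count and percentage. This is a fair reading, perhaps the more natural one, so the impossible limits are conditional and not a planned output. It does not remove the gap, because on this reading the percentages have no interval at all. The other reading also has some support, since the paragraph opens by covering all secondary variables.

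A second reply is that the restriction is deliberate: the study is exploratory, sized on feasibility, and shows each percentage beside placebo, so a crude difference can be found by subtraction. That stands as a reason not to ask for a test. With assumed rates of 10% versus 40%, approximate power is only 54% for 27 versus 15 and 42% for 9 versus 15. It is not a reason to omit an estimate with an interval, because the same exploratory plan gives one for the continuous scores.

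A reader might also infer that the secondary objectives go unanswered as a whole. The documents do not support that. UCEIS, total Mayo and partial Mayo each get a difference from placebo with a CI. The mean mMES change at the non-recommended doses, the main secondary endpoint, is compared with placebo under SAP 7.1. Mean Baron scores are also summarised by treatment, though without a comparison.

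**Conclusion.** The point holds, within limits. Five of eight Week 12 secondary variables have no planned difference from placebo and no interval method suited to a proportion, in either document. The objectives affected are those resting on percentages: Baron improvement, mucosal healing, clinical response and clinical remission. The remaining percentage, mMES improvement, has a mean-change counterpart that is compared with placebo.

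A reader might infer that the plan prescribes a t interval for percentages and that it fails at every result. Neither follows. The cross-reference is ambiguous, and the failure is confined to 1–3 responders or non-responders and to 0 or n. It matters most in the 9-subject groups and in placebo at low rates. For 11/27 the 7.1 formula gives 20.9% to 60.5%, close to the exact 22.4% to 61.2%.

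The group sizes are the plan's own; the counts and rates are assumptions. This is a cheap improvement to the reporting plan and does not affect the primary analysis.

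**What to change.** In SAP 7.2, state that the 7.1 interval formula applies only to mean changes. For each of the five binary Week 12 endpoints, specify:

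- a 95% CI per arm, exact or Wilson, with one method named in advance;
- the difference from placebo for each dose level with a Newcombe 95% CI, labelled exploratory and without a test.

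Put these in Table 14.2-2.4 and in the unblinded Week 12 Table 14.2.2.4. Settle the denominator at the same time: SAP 4.1 uses subjects with a reported value, while SAP 4.4 uses the number of subjects in the group.

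The cost is a few table columns and a short SAP edit, with no new data. The intervals will be wide, as the assumed 11/27 versus 3/15 example shows, and the tables should present them as a measure of uncertainty and not as a pass or fail criterion.
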